After the PK run-in period, the treatment period for the first 15 patients will start on Cycle 1 Day 1 in which LDK378 will be given as continuous daily oral dosing at 750 mg QD in 28-day cycles. Apart from these 15 patients, the rest of the enrolled patients will start treatment with LDK378 at 750 mg QD on Cycle 1 Day 1 in 28-day cycles as phase II component of the study.

Data from all patients entering the 28-day cycles treatment period will be used to characterize the PK profile, safety and tolerability of LDK378 as continuous 750 mg once daily dose as well as to demonstrate the antitumor activity of LDK378 as measured by ORR by investigator assessment.

[figure not shown]
[figure not shown]

Figure 4-1 Study Design

Patients will take LDK378 once daily, at approximately the same time each day in the morning. On days when a PK sample is obtained, the patient will take LDK378 during the clinic visit as instructed by the study staff. Treatment with LDK378 will continue until the patient experiences unacceptable toxicity that precludes further treatment, discontinues treatment at the discretion of the patient or investigator, starts a new anti-cancer therapy or dies. Clinical and laboratory assessments will be performed as described in [Section 7](#). If the patient experiences RECIST-defined progressive disease (PD) on LDK378 as assessed by the investigator, treatment with the study drug may be continued if, in the judgment of the investigator, there is still evidence of clinical benefit. These patients will be counted as PD for ORR, DOR, DCR and PFS calculations.

Tumor response will be evaluated every 8 weeks (i.e. every 2 cycles) starting from the first day of treatment with LDK378 until the time of RECIST-defined PD by investigator assessment, withdrawal of consent for further follow-up, loss to follow-up or death. This schedule of tumor assessment must continue regardless of dose interruptions. In patients who discontinue treatment in the absence of progression, tumor assessments will continue every 8 weeks until progression of disease, withdrawal of consent for further follow-up, loss to follow-up or death.

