7.1.7.3 Survival follow-up

All patients who progressed (PD) as per investigator assessment, have started a new anti-neoplastic therapy, and/or withdrew consent from further study assessments will subsequently be followed for survival information every 12 weeks until death, lost to follow-up or withdrawal of consent for survival. The investigator or his designee will collect this survival information and any new anti-neoplastic therapies for all patients until the final survival analysis.

Follow-up can be done via a phone contact. Antineoplastic therapies will be captured on the 'Antineoplastic therapies since discontinuation of study treatment' eCRF page following the last dose of the study treatment.

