10.5.2.1 Endpoint and analysis for other secondary objectives

Duration of response

Among patients with a confirmed response (PR or CR) per RECIST 1.1, duration of response (DOR) is defined as the time from first documented response (PR or CR) to the date of first documented disease progression or death due to any cause. DOR will be listed by patient and described using Kaplan-Meier curves and relevant statistics. Censoring rules for DOR follow those for PFS below.

Disease control rate

The disease control rate (DCR), defined as the proportion of patients with best overall response of CR, PR, or SD per RECIST 1.1 will be estimated and the 95% CI based on the exact binomial distribution will be provided.

[figure not shown]
Time to response

Time to response (TTR) is defined as the time from the date of the first dose of LDK378 to first documented response (CR or PR, which must be confirmed subsequently) per RECIST 1.1 for patients with a confirmed PR or CR. TTR will be described using appropriate summary statistics.

Progression-free survival

Progression-free survival (PFS) is defined as the time from the date of first dose of LDK378 to the date of first documented disease progression per RECIST 1.1 or death due to any cause.

A patient who has not progressed or died at the date of the analysis or when he/she receives any further anticancer therapy in the absence of disease progression will be censored at the time of the last adequate tumor evaluation before the earlier of the cut-off date or the

anticancer therapy date. By default, if disease progression or death is documented after one single missing tumor evaluation, the actual event date of disease progression/death will be used for the PFS event date. If disease progression or death is documented after two or more missing tumor evaluations, the PFS time of these patients will be censored at the date of the last adequate tumor evaluation without PD.

PFS assessed by the investigators will be described using Kaplan-Meier methods and appropriate summary statistics.

Overall survival

Overall survival (OS) is defined as the time from the date of first dose of LDK378 to the date of death due to any cause. OS time for patients who are alive at the end of the study or are lost to follow-up will be censored at the date of last contact.

OS will be described using Kaplan-Meier methods and appropriate summary statistics.

Overall intracranial response rate (OIRR)

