3.2.10.2 Other secondary efficacy objectives

The other secondary efficacy objectives are:

- To evaluate DOR, DCR, TTR, OIRR and PFS both by investigator assessment and BIRC assessment
- To evaluate ORR and OIRR by BIRC
- To evaluate OS

Duration of Response

Among patients with a confirmed response (PR or CR) per RECIST 1.1 by investigator, DOR is defined as the time from first documented response (PR or CR) to the date of first documented disease progression or death due to any cause. If a patient has not had an event, DOR is censored at the date of last adequate tumor assessment.

The censoring and event date options to be considered for the DOR analysis follow those for PFS below.

DOR will be described in tabular and graphical format using Kaplan-Meier methods including estimated median (in months) with 95% CI, 25th and 75th percentiles ([Brookmeyer and Crowley 1982](#), [Klein and Moeschberger 1997](#)) and Kaplan-Meier estimated probabilities with corresponding 95% CIs ([Kalbfleisch and Prentice 1980](#)) at several time points (including at least 3, 6, 9, 12, 15 and 18 months).

Refer to [Section 4.2.3.3](#) for further details regarding derivation of Kaplan –Meier estimates.

Disease control rate

DCR, defined as the proportion of patients with best overall response of CR, PR, SD, or Non-CR/Non-PD per RECIST 1.1 by investigator will be estimated and the 95% CI ([Clopper & Pearson, 1934](#)) based on the exact binomial distribution will be provided.

Time to response

Time to overall response of CR or PR (TTR) is defined as the time from start of study drug to first documented response (CR or PR, which must be confirmed subsequently) for patients with a confirmed CR or PR.

TTR will be summarized in 2-month intervals using descriptive statistics. The analysis will be performed based on investigator assessment.

Progression-free survival

PFS is defined as the time from the date of first dose of study drug to the date of the first documented disease progression per RECIST 1.1 by investigator, or death due to any cause.

If a patient has not progressed or is not known to have died at the date of analysis cut-off or has received any anticancer therapy other than study drug, PFS will be censored at the date of the last adequate tumor evaluation before the cut-off date or before the start of the new anticancer therapy date, whichever is earlier. Clinical deterioration will not be considered as a qualifying

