event for progression. Refer to [Table 3-3](#) for censoring and event date options and outcomes for PFS.

In particular, PFS will be censored at the last adequate tumor assessment if one of the following occurs: absence of event; the event occurred after a new anticancer therapy is given; the event occurred after two or more missing tumor assessments (see [Section 4.2.1](#)). See also [Section 4.2.1](#) describing the special case of a missing baseline tumor assessment.

PFS will be described in tabular and graphical format using Kaplan-Meier methods as described for DOR, including estimated median (in months) with 95% CI, 25th and 75th percentiles and Kaplan-Meier estimated probabilities with corresponding 95% CIs at several time points (including at least 3, 6, 12, 18 and 24 months). Censoring reasons will also be summarized (see [Section 4.2.1](#))

Table 3-4 Outcome and event dates for PFS and DOR analyses

Situation	Date	Outcome
A No baseline assessment	Date of first dose of study drug ^a	Censored
B Progression at or before next scheduled Assessment	Date of progression	Progressed
C1 Progression or death after exactly one missing assessment	Date of progression (or death)	Progressed
C2 Progression or death after two or more missing assessments	Date of last adequate assessment	Censored
D No progression	Date of last adequate assessment	Censored
E Treatment discontinuation due to 'Disease progression' without documented progression, i.e. clinical progression based on investigator claim	N/A	Information ignored. Outcome derived based on radiology data only.
F New anticancer therapy given	Date of last adequate assessment	Censored

^aThe rare exception to this is if the patient dies no later than the time of the second scheduled assessment as defined in the protocol in which case this is a PFS event at the date of death

In addition, summary tables of PFS by brain metastasis at baseline status (presence vs. absence) will be generated by investigator and BIRC assessment respectively.

Overall survival

OS is defined as the time from the first dose of study drug to the date of death due to any cause. If the patient is alive at the date of the analysis cut-off or lost to follow-up, then OS will be censored at the last contact date prior to data cutoff date (see [Section 4.1.4](#) for further details on derivation of last contact date).

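### PFS and DOR drop every event after new anticancer therapy or after two missed scans, and no visible sensitivity analysis shows how far the estimates depend on this

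*SAP*

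**What the plan says.** **Censoring at new therapy.** Under SAP 3.2.10.2, if a patient "has received any anticancer therapy other than study drug, PFS will be censored at the date of the last adequate tumor evaluation" before the data cut-off or the start of the new therapy, whichever is earlier. Table 3-4 row F repeats this.

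**Censoring after missed scans.** Table 3-4 has the row "C2 Progression or death after two or more missing assessments", with the outcome censored at the last adequate assessment. The text above the table gives both conditions together: "the event occurred after a new anticancer therapy is given; the event occurred after two or more missing tumor assessments". Protocol 10.5.2.1 agrees: "If disease progression or death is documented after two or more missing tumor evaluations, the PFS time of these patients will be censored". It also censors at further anticancer therapy.

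**DOR.** The SAP states: "The censoring and event date options to be considered for the DOR analysis follow those for PFS below".

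**Scanning.** Starting new therapy ends study treatment. Protocol 4.1 continues treatment until, among other reasons, the patient "starts a new anti-cancer therapy or dies". For patients who stop without progression, the same section says that "tumor assessments will continue every 8 weeks until progression of disease, withdrawal of consent for further follow-up, loss to follow-up or death". New therapy is not among the stop reasons there, in protocol 7.2.1.2 or in SAP 2.4.

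**A competing instruction.** Protocol 7.1.7.3 lists patients who "have started a new anti-neoplastic therapy" among those then followed for survival every 12 weeks. Protocol 14.2.4.3 lists new therapy for the study indication as a reason for study-phase completion.

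**Supportive analyses.** The last part of SAP 3.2.10.2 repeats the time-to-event analyses on the BIRC reading with the same conventions. It also plans PFS tables by baseline brain metastasis. Censoring reasons, follow-up time and gap time are summarised.

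**The concern.** A patient who switches without RECIST progression is often switching for a reason. SAP 3.2.10.2 does not accept clinical deterioration as progression, and Table 3-4 row E sets aside progression claimed by the investigator without documentation. A patient who worsens and changes therapy is therefore censored at the last scan, although probably close to an event.

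The missed-scan rule also reaches further than its name suggests. SAP 4.2.1 treats a scan read as unknown as missing, and by default a change of contrast or technique makes the reading unknown. A death with an exact date is removed from PFS if it falls more than 18 weeks after the last adequate scan.

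Kaplan-Meier estimation assumes that censored patients have the same future risk as those still followed. If these patients are at higher risk, both curves sit too high. Protocol 2.1 and 2.2 say the study supports registration in China. Protocol 2.2 calls PFS an important supportive endpoint and uses DOR to supplement ORR. Protocol 1.3 sets an earlier ceritinib median of 6.7 months beside external medians of 7.7, 4.2 and 2.6 months. On that scale a shift of a month or two could change the reading.

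**Working it through.** **1. The plan's own threshold.** SAP 4.2.1 gives an 8-week interval and a total window of 2 weeks.
- One missed scan: 8 + 2 = 10 weeks.
- Two missed scans: (2 × 8) + 2 = 18 weeks.

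Both reproduce.

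**2. Does any planned output count the removed events?**
- The BIRC analysis keeps the same censoring.
- The brain-metastasis tables describe no change of rule.
- In the censoring-reason table (SAP 4.2.1), reason 6 counts events removed after two or more missed scans.
- Reason 5 counts patients censored for new therapy, but not whether they later progressed or died. Reason 4 takes precedence over it when the gap since the last adequate scan reaches the 18-week threshold.
- OS uses the deaths, but not the progressions.

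So the number of patients affected can largely be seen. The effect on the PFS and DOR curves cannot.

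**3. Size, simple model.** The documents do not give the share q of events pre-empted by a switch or missed scans, so q is assumed. With a constant hazard, censoring a share q of patients just before their event multiplies the hazard by (1 − q), so the median becomes median/(1 − q). The starting medians are those for patients with a prior ALK inhibitor in protocol 1.2.1.2.2.

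| Assumed q | PFS, from 6.90 months | DOR, from 7.39 months |
|---|---|---|
| 5% | 6.90/0.95 = 7.26 | 7.39/0.95 = 7.78 |
| 10% | 6.90/0.90 = 7.67 | 7.39/0.90 = 8.21 |
| 20% | 6.90/0.80 = 8.62 | 7.39/0.80 = 9.24 |
| 30% | 6.90/0.70 = 9.86 | 7.39/0.70 = 10.56 |

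**4. Size, simulated Kaplan-Meier PFS.** Assumptions: 103 patients (the number treated), exponential times with median 6.90 months, scans every 8 weeks with 7 days either way, 24 months of follow-up and 1,000 runs. Each pair is all events counted, then the SAP rule.

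| Scenario | PFS at 6 months | PFS at 12 months |
|---|---|---|
| Informative switching, 10% | 0.576 vs 0.604 | 0.330 vs 0.363 |
| Informative switching, 20% | 0.576 vs 0.633 | 0.330 vs 0.399 |
| Informative switching, 30% | 0.573 vs 0.664 | 0.331 vs 0.443 |
| 10% of events after two missed scans, no switching | 0.601 vs 0.601 | 0.342 vs 0.360 |
| Switching unrelated to prognosis, 10% | 0.572 vs 0.568 | 0.329 vs 0.326 |

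The 6- and 12-month probabilities are shown because simulated medians jump from one scan date to the next. Informative switching drives the effect. Missed scans alone at 10% add little, and non-informative switching produces no overstatement.

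**The case against.** The strongest reply has four parts.

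- **The rule is planned and consistent.** Protocol 10.5.2.1 and the SAP agree on it. PFS and DOR are descriptive, and protocol 10.10 says the study is not powered for formal testing. ORR counts only responses before new therapy, and OS is not censored at a switch. All of this stands, and it is why Table 3-4 should remain the main analysis.
- **Some of these progressions are caught.** Protocol 7.2.1.2 requires imaging at the end-of-treatment visit, which protocol 4.1 places within 7 days of the last dose. RECIST progression found there before a switch counts. This reduces the number affected, but a patient who worsens without meeting RECIST criteria is still censored.
- **The post-switch scans may be incomplete.** Protocol 7.1.7.3 and 14.2.4.3 point away from continued scanning. The protocol's summary of changes shows that new therapy was dropped as a reason to stop scans only after recruitment was complete. A reader might infer that all the data are already in hand, but the documents do not support that. Deaths are collected in survival follow-up, so part of the analysis is feasible in any case.
- **The alternative is not clean.** Progression after a switch partly reflects the next therapy, and progression found after a long gap is dated late. The sensitivity estimate is therefore a second view of the data, not a corrected value, and it need not be lower.

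**Conclusion.** The point holds as a conditional one. The rules remove events from PFS and DOR in circumstances plausibly related to prognosis, and no visible analysis shows the consequence. With assumed informative shares of 10% to 30%, a 6.9-month median PFS would read about 0.8 to 3.0 months longer. With non-informative switching the shift is essentially nil. The illustration rests on a constant hazard, on affected patients being about to have an event, and on 6.9 months being the median with all events counted.

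Three stronger readings are not supported:
- **That PFS and DOR are biased upward.** This depends on why patients switch or miss scans, which the documents do not say.
- **That 9.9 months is an upper bound.** The shares are assumptions, and nothing caps them at 30%.
- **That no alternative analysis exists.** Parts of the documents are redacted. Protocol Table 14-9, which both documents cite on censoring, is not in the text available here. The most that can be said is that none is visible.

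**What to change.** 1. Keep Table 3-4 as the main analysis.
2. Add to SAP 3.2.10.2 one sensitivity analysis of investigator-assessed PFS and DOR. It should count every RECIST progression or death at its recorded date, regardless of new therapy or missed scans. Protocol 14.2.4.1 asks for such analyses to be documented before database lock.
3. Report how many progressions and deaths row C2 and row F each remove, for each endpoint.
4. Reconcile protocol 7.1.7.3 and 14.2.4.3 with 4.1 and 7.2.1.2 on tumor follow-up after new therapy starts. Report how complete the post-switch scans are, so that the sensitivity result can be weighed.

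The cost is one extra table and curve per endpoint, with no new patients and no change to the main result. The sponsor should expect that the estimate may be lower, that post-switch scans may be incomplete, and that progression after a switch partly reflects the next therapy. Label: cheap improvement.

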4.3 Definition of end of the study

The primary data analysis will be performed after all patients have undergone at least 24 weeks (6 cycles) of treatment with LDK378 or have discontinued earlier. At this time, the primary clinical study report (CSR) will be produced. Following the primary analysis time point, the study will remain open. Patients still being followed on the study, either still on treatment, efficacy follow up post-treatment discontinuation in the absence of PD, or in survival follow up, will continue as per the schedule of assessments.

The study will end once at least 75% of patients have died, have been lost to follow-up or have withdrawn consent for survival follow-up. The final analysis of study data will be conducted at the end of the study. All available data from all patients up to this cutoff date will be analyzed.

At the end of study (EOS), the patients who are still receiving treatment with LDK378 because they have continuing CR, PR or SD or because they are deriving clinical benefit in the opinion of the investigator despite having a RECIST 1.1 defined progressive disease will be offered enrollment into a separate protocol. In this protocol, Novartis will continue to supply LDK378 to patients who may benefit from continued treatment as per the Investigator's opinion and safety will be monitored and reported to Health Authorities per regulatory requirements. Prior to the end of the current study ([\[CLDK378A2109\]](#)), the separate protocol will be submitted to Health Authorities and IRBs involved in the current study.

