OS will be described in tabular and graphical format using Kaplan-Meier methods as described for DOR, including estimated median (in months) with 95% CI, 25th and 75th percentiles and Kaplan-Meier estimated probabilities with corresponding 95% CIs at several time points

(including at least 3, 6, 12, 18 and 24 months). Censoring reasons ('Alive' or 'Lost to follow-up') will be summarized. Patients not known to have died will be censored for 'Lost to follow-up' if the time between their last contact date and the analysis cut-off date is longer than four cycles plus 2 weeks, i.e., 18 weeks for this study.

Overall intracranial response rate

OIRR is calculated based on response assessments in the brain for patients 1) having both measurable and/or non-measurable brain metastases at baseline (i.e. at least one target/and or non-target lesion in the brain); 2) having measurable brain metastases at baseline (i.e., at least one target lesion in the brain). OIRR is defined as the proportion of patients with a best overall confirmed response of CR or PR in the brain, as assessed per RECIST 1.1 by the investigator.

OIRR will be estimated and the 95% CI based on the exact binomial distribution will be provided. For details on the OIRR calculations see [section 4.2.4](#).

The following analyses will be performed:

- Best overall intracranial response per investigator assessment (Full analysis set - Patients with measurable and/or non-measurable disease in the brain at baseline as per investigator review)
- Best overall intracranial response per investigator assessment (Full analysis set – patients with measurable disease in the brain at baseline as per investigator review)

Supportive analyses

DOT, DCR, TTR, PFS and OIRR will also be assessed by BIRC using the same analytical conventions as analysis by investigator assessment and serve as the basis of supportive analysis.

Duration of Follow-up and Gap Analyses

Follow-up in the study will be summarized using the following methods to provide a comprehensive assessment of follow-up for all patients.

Summary of duration between start date of study drug and cut-off date, and follow-up times for PFS/OS, are defined as follows:

- Duration between start date of study drug and data cut-off date = (Cut-off date – Start date of study drug + 1) / 30.4375 (months).

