- Follow-up time = (Date of event or censoring – Start date of study drug + 1) / 30.4375 (months) regardless of censoring. Date of censoring is defined as the last adequate tumor assessment date for PFS or last contact date (when the patient is known as alive) for OS.

Summaries will also be tabulated for the gap time for PFS/OS follow-up compared to the cutoff date. Gap analysis is the summary of gap time (months) for PFS/OS follow-up as compared to cut-off date. Gap time for PFS/OS is defined as follows

- For patients who are censored regardless of follow-up status,
Gap time = (data cut-off date – censoring date)/30.4375 (months).

- For patients who completed study phase or prematurely discontinued from the study due to certain reasons e.g. withdraw consent, lost to follow-up,

[figure not shown]
Gap time = (min(data cut-off date, study discontinuation date)- censoring date)/30.4375 (months).

- For patients who are censored but still in follow-up,
Gap time = (data cut-off date – censoring date)/30.4375 (months).

Quartiles, minimum and maximum as well as the frequency count and percentage of patients in each of <4, 4-<8, 8-<12, 12-<18, \geq 18 months will be reported for PFS and OS gap time for patients who were censored.

All summaries will be reported in months (see Section 4.1.5). The calculations for PFS will be based on investigator assessment. Date of censoring is the same as defined for the PFS and OS analysis.

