4.5.2 First interpretable results for primary analysis

- Table of demographics and other baseline characteristics
- Table of subject disposition
- Table of analysis sets
- Table of disease history
- Table of Prior antineoplastic therapy overall and on Crizotinib
- Table of duration of exposure and relative dose intensity
- Table of summary of PK parameters for LDK378
- Figures of geometric mean and arithmetic mean (SD) trough concentration-time profiles for LDK378
- Figure of geometric mean and arithmetic mean (SD) concentration-time profiles for LDK378
- Overall summary of adverse events and clinically notable AEs
- Adverse events (at least xx%), regardless of study drug relationship, by preferred term and maximum grade
- SAE and death information provided in text
- Table of ALT, AST, ALP and total bilirubin abnormalities
- Table of notable ECG values
- Best overall response per investigator and BIRC assessment
- Best overall intracranial response and duration of response per investigator and BIRC assessment
- Progression free survival per investigator and BIRC assessment
- Summary of duration between start of treatment and cut-off date, and follow-up time for long-term outcomes

5 Reference:

Gehan EA, George SL (1970) Cancer Chemother Rep 54:225-235

Allison PD (2000). Survival analysis using the SAS system. Cary, NC, SAS Institute Inc.

Brookmeyer R and Crowley J (1982). A Confidence Interval for the Median Survival Time, *Biometrics* 38, 29 - 41.

Clopper CJ, Pearson ES (1934). The use of confidence or fiducial limits illustrated in the case of the binomial. *Biometrika*; 26, 404-413.

Collett D (1994). Modelling survival data in medical research. London, Chapman & Hall.

Dmitrienko A et al. (2005). *Analysis of clinical trials using SAS*. SAS Institute Inc., SAS press.

Fayers PM et al., on behalf of the EORTC Quality of Life Group (2001). The EORTC QLQ-C30 Scoring Manual (3rd Edition). Published by: European Organisation for Research and Treatment of Cancer, Brussels.

FDA (2007). Guidance for Industry Clinical Trial Endpoints for the Approval of Cancer Drugs and Biologics, US Department of Health and Human Services.

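### The SAP's follow-up time is event-or-censoring time, no measure is named as median follow-up, and the gap-time rules overlap

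*SAP*

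**What the plan says.** The duration-of-follow-up part of SAP 3.2.10.2 states its aim: "Follow-up in the study will be summarized using the following methods to provide a comprehensive assessment of follow-up for all patients". It then defines two quantities for every patient:

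- Potential follow-up: "Duration between start date of study drug and data cut-off date = (Cut-off date – Start date of study drug + 1", converted to months.
- Follow-up time: "Follow-up time = (Date of event or censoring – Start date of study drug + 1) / 30.4375 (months) regardless of censoring". The censoring date is the last adequate tumour assessment for PFS and the last contact for OS.

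SAP 4.5.2 lists both among the first results of the primary analysis: "Summary of duration between start of treatment and cut-off date, and follow-up time for long-term outcomes". SAP 3.2.1 summarises quantitative variables by plain descriptive statistics, including the median. The SAP names no reverse Kaplan-Meier estimate.

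Gap time has three bullets:

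1. "For patients who are censored regardless of follow-up status": cut-off minus censoring date.
2. "For patients who completed study phase or prematurely discontinued from the study due to certain reasons e.g. withdraw consent, lost to follow-up": the earlier of cut-off and study discontinuation, minus censoring date.
3. Censored patients still being followed: the same formula as bullet 1.

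Quartiles, range and five bins, from under 4 to at least 18 months, are then planned for censored patients. The section does not say which bullet supplies the values.

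Protocol 4.3 sets the end of the study: "The study will end once at least 75% of patients have died, have been lost to follow-up", or have withdrawn from survival follow-up.

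**The concern.** A patient who dies at month 3 contributes 3 months to follow-up time, however complete the follow-up was. The median of this quantity therefore moves with the outcome. Potential follow-up has the opposite weakness: it credits patients who were lost or withdrew with observation up to the cut-off.

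In a single-arm trial intended to support registration in China (Protocol 2.1), readers judge the maturity of PFS and OS from the stated median follow-up. If the SAP leaves open which figure carries that name, two very different numbers could both be defended. The gap table is meant to show how current the censored patients are, and it depends on a rule that the SAP does not fix.

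**Working it through.** **Inputs from the documents.** 103 patients treated (Protocol, Amendment 3 rationale). Final cut-off when 75% have died, been lost or withdrawn (Protocol 4.3). Illustrative PFS median of 6.9 months in patients with a prior ALK inhibitor (Protocol 1.2.1.2.2). A month is 365.25/12 = 30.4375 days, which reproduces SAP 4.1.5. The documents give no follow-up figure to reproduce.

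**Assumptions, not in the documents.** OS median 12, 18 or 24 months; uniform accrual over 12 months; exponential survival and loss; a share *s* of competing exits being loss (0%, 10%, 25% or 40%). There were 600 simulated trials per setting.

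**What the planned median estimates.** Let λ be the death hazard and μ the loss hazard, with μ = λs/(1−s). Then λ + μ = λ/(1−s), and the median time to death or loss is (1−s) × median OS. For a 12-month OS median this gives:

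- s = 0: 12.0
- s = 10%: 0.90 × 12 = 10.8
- s = 25%: 0.75 × 12 = 9.0
- s = 40%: 0.60 × 12 = 7.2

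The simulation agrees. All figures are medians in months:

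| OS median | Loss share | SAP follow-up time | Reverse Kaplan-Meier | First dose to cut-off |
|---|---|---|---|---|
| 12 | 0% | 12.0 | 24.5 | 24.3 |
| 18 | 0% | 18.0 | 36.6 | 36.4 |
| 24 | 0% | 23.9 | 48.4 | 48.0 |
| 12 | 25% | 9.0 | 16.5 | 18.6 |
| 18 | 25% | 13.5 | 25.5 | 27.5 |
| 24 | 25% | 18.1 | 34.4 | 36.5 |

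**1% loss per month, 15-month accrual.** For OS medians of 12 and 18 months, SAP follow-up time is 10.3 and 14.4. Reverse Kaplan-Meier gives 19.9 and 27.1, and first dose to cut-off gives 21.2 and 29.5. The excess of the last measure over reverse Kaplan-Meier is 21.2/19.9 = 1.07 and 29.5/27.1 = 1.09.

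**PFS at the primary cut-off** (15-month accrual, cut-off 24 weeks after last entry, no loss). SAP follow-up time is 6.3, reverse Kaplan-Meier 13.1 and first dose to cut-off 12.9. The SAP's PFS censoring rules are not modelled here.

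**Gap time, PFS example.** Last adequate scan on day 183, lost on day 274, cut-off on day 731.

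- Bullet 1: (731 − 183)/30.4375 = 18.0 months, the highest bin.
- Bullet 2: (274 − 183)/30.4375 = 3.0 months, the lowest bin.

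**Gap time, OS.** SAP 4.1.4 includes the discontinuation dates from the treatment and post-treatment disposition pages among the dates that define last contact. If study discontinuation means one of these dates, a patient lost on day 183 has last contact on day 183. Bullet 1 then gives (731 − 183)/30.4375 = 18.0 months and bullet 2 gives 0. Protocol Appendix 2, section 14.2.4.3, places study-phase completion before survival follow-up. If bullet 2 uses that completion date, a patient contacted later has a censoring date after it, and the gap is negative.

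**The case against.** The strongest reply is that the SAP already plans a good measure. First dose to cut-off is reported for every patient beside follow-up time, and without loss it is within about 1% of reverse Kaplan-Meier. This stands. A reader might infer that the trial's reported median follow-up will simply be its median survival, but the documents do not support that. No section gives follow-up time that role, and the 75% trigger counts loss and withdrawal as well as deaths, so the figure can also fall well below median survival.

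Time to event or censoring is also literally the observed time for that endpoint. It is a legitimate description, and the fault lies in its label and in the lack of a named headline measure.

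The gap bullets have a coherent reading: bullet 1 as an all-censored summary, bullets 2 and 3 as a breakdown by status. Two values for one patient would then be intended. The SAP does not say so, and does not say which set feeds the quartiles and bins.

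Nor are lost patients hidden, as one might conclude from bullet 2. The OS and PFS censoring-reason tables show loss. However, OS loss is declared when last contact is more than 18 weeks before cut-off (18 × 7/30.4375 = 4.1 months), and under bullet 2 the same patient can sit in the under-4-month gap bin.

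Reversing the PFS indicator is not free of interpretation either. PFS is censored at new therapy and after two or more missed assessments, although Protocol 4.1 continues scans until progression.

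**Conclusion.** The point holds as a defect of descriptive reporting. Follow-up time tracks the outcome. With no loss it is about half the reverse Kaplan-Meier figure for OS (12.0 against 24.5, 18.0 against 36.6) under the assumed survival and accrual. First dose to cut-off is fair when loss is small and about 7-9% too long at 1% monthly loss. The SAP does not choose between them. Read literally, the gap bullets give a censored patient who left before the cut-off two values, which can fall in opposite bins; zero or negative OS gaps depend on what study discontinuation means.

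The sizes rest on exponential times and on OS medians, accrual and loss rates that the documents do not give. The direction follows from the definitions. Kaplan-Meier estimates and intervals for PFS and OS are unaffected, and both are secondary endpoints, so this is a desirable correction and not a threat to the trial's conclusions.

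**What to change.** In SAP 3.2.10.2 and 4.5.2:

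- Relabel the current follow-up time as observed time.
- Report reverse Kaplan-Meier median follow-up with 95% CI and quartiles for OS, and name it as the study's median follow-up.
- Report the same for PFS, with a note that censoring at new therapy or after two or more missed assessments counts as end of follow-up.
- Keep first dose to cut-off, labelled as potential follow-up.
- Compute gap time as cut-off minus censoring date for all censored patients, tabulated separately for those who left the study and those still followed.

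The cost is SAP wording, one LIFETEST call per endpoint with the censoring indicator reversed, and an extra table row. No new data are needed. The small downside is a follow-up figure that may look less favourable than first dose to cut-off.
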